2.3 Sample Size

2.4 Selection and Withdrawal of Subjects

2.4.1 Inclusion Criteria

Subjects must meet the following inclusion criteria:

1. Adult subjects, men and women, defined by age ≥ 18 years at the time of screening.
2. Pathologically proven and clinically confirmed T1 (< 2 cm) or T2 (> 2 cm but ≤ 4 cm) SCC of the lip or oral cavity (anterior 2/3 of the tongue, floor of mouth, lower and upper gingiva, salivary gland, hard palate, and buccal mucosa).
3. Tumor must be easily accessible, with no evidence of infection or active bleeding, encroaching major vessels or clinical evidence of neural invasion. Tumors should not have been previously irradiated.
4. Tumor must be amenable to surgical resection no later than 42 days post Visit 1.
5. Clinically and/or radiologically measurable tumor.
6. Eastern Collaborative Oncology Group Performance Status of ≤ 2 .
7. Adequate renal function as demonstrated by renal creatinine clearance ≥ 50 mL/min (calculated using the Cockcroft-Gault formula).
8. Adequate organ function defined as: ANC $\geq 1000/\mu\text{L}$, platelet $\geq 100,000/\mu\text{L}$; hemoglobin ≥ 9.0 g/dL; AST and ALT ≤ 2.5 times the upper limit of normal (ULN), serum bilirubin ≤ 1.5 times the ULN or direct bilirubin $\leq \text{ULN}$ for subjects with total bilirubin > 1.5 times the ULN.
9. Candidates for standard of care treatment consisting of surgery.
10. Male and female subjects of childbearing potential must agree to use 2 methods of effective contraception from screening and for at least 30 days after the final dose of investigational product. Appropriate birth control is defined as barrier methods with spermicides, oral or parenteral contraceptives and/or intrauterine devices, or naturally or surgically sterile (with documentation in the subject's medical records). Postmenopausal women are defined as presenting at least 12 months' natural spontaneous amenorrhea, or at least 6 weeks following surgical menopause (bilateral oophorectomy). Females of childbearing potential must be non-lactating and have a negative serum hCG within 14 days of treatment initiation.
11. Absence of any serious underlying medical conditions which could impair the ability of the subject to participate in the study.

12. Have a life expectancy of ≥ 3 months.
13. Willing and able to provide written informed consent.
14. Able to return to study site for treatment and follow-up visits as defined in the Protocol.

2.4.2 Exclusion Criteria

Subjects meeting any of the following criteria will be excluded from the study:

1. Known distant metastasis of the SCC of the oral cavity
2. Prior radiation and/or systemic chemotherapy for the treatment of SCC of the head and neck less than 2 years prior to screening
3. Concurrent malignancy, with the exception of localized squamous cell carcinomas of the skin
4. Exposure to any investigational agent within 3 months prior to screening
5. Known allergy or hypersensitivity to platinum-containing agents, or known intolerance to a prior platinum-containing agent, or to any of the excipients, which, in the judgement of the physician will preclude re-exposure to platinum-containing agent
6. Active, uncontrolled infection requiring systemic therapy, such as but not limited to HIV, Hepatitis B or C
7. Uncontrolled intercurrent illness that would risk subject safety, interfere with the objectives of the protocol, or limit subject compliance with study requirements, as determined by the Investigator
8. Known or suspected pregnancy, planned pregnancy, or lactation
9. Any medical or psychiatric condition that may compromise the ability to give written informed consent

2.5 Criteria for Individual Subject Discontinuation of Protocol Therapy

Subjects should be discontinued from protocol therapy, while follow-up as per protocol, for the following reasons:

- Completion of the scheduled PRV111 therapy
- Meets 1 of the stopping rules for an individual subject
- Pregnancy
- Noncompliance with trial or follow-up procedures
- Withdrawal at the Investigator's request for any reason that the Investigator believes continuation of study drug therapy would not be in the subject's best interest
- Subjects may be withdrawn at any time for drug intolerability, disease progression, availability of other therapeutic options, or subject judgment

2.6 Criteria for Individual Subject Discontinuation from the Trial

Subjects may withdraw from further participation in the study at any time and for any reason without prejudice. The degree to which a subject withdraws can vary and efforts will be made to collect important safety data if feasible and the subject agrees. A subject will be considered to be withdrawn from the trial for the following reasons:

- Withdrawn consent from all treatment and follow-up

- Death
- Lost to follow-up
- Termination of the trial by the Sponsor

2.7 Handling of Subject Withdrawals or Subject Discontinuation of Study Intervention

If a subject withdraws consent for the treatment, the Investigator will make every effort to complete all final evaluations and procedures required by the Protocol. The subject will be asked to return to the clinic for a follow-up visit to assess overall safety prior to study completion. In the event a subject withdraws for safety reasons (adverse event/serious adverse event [AE/SAE], National Cancer Institute's (NCI) Common Terminology Criteria for Adverse Events [CTCAE] toxicity related events, etc.), every effort will be made to continue to follow-up with the subject until the documented condition resolves to protocol-established grades.

The reasons for discontinuation of dosing must be clearly documented on the case report form (CRF).

2.8 Replacement of subjects

Subjects will not be replaced.

2.9 Treatments Administered

a. Description of Test Product

PRV111 (Cisplatin Transmucosal System) (referred to as PRV111) consists of:

- PRV111 4 cm² patch containing 2 mg of cisplatin (0.5 mg/cm²) backed with a pressure sensitive acrylic adhesive non-woven fabric backing.
- PE Powder for Reconstitution [REDACTED]

[REDACTED]
[REDACTED]
[REDACTED]

b. Dosing and Administration

Each treatment visit will include 1 mL application of the PE. Starting 5 minutes after application of the PE, 1 or 2 patches (depending on tumor size) will be applied. For Stage 1, a total of 3 treatment applications of patches will occur. These successive applications will span approximately 35 minutes. The 3 applications provide a total of 6 mg of cisplatin per visit (12 mg if 2 patches are applied at the same time).

In Stage 2 (Stage 2a and Stage 2b), subjects will receive 2, 3, or 5 treatment applications at each of the 4 planned treatment visits, depending on the results of Stage 1.

Refer to the Pharmacy Manual for detailed instructions on applying the PRV111 patches.

Table 1 presents definition used for dosing and treatment in this study. Treatment is expected to be approximately 35 minutes for each treatment visit.

Table 1. Dosing Terminology

Term	Definition
Treatment visit	Two to 6 days apart, during which PRV111 patches will be administered.
Treatment application	Three patch applications will occur during each treatment visit in Stage 1. Two, 3, or 5 patch applications will occur during each treatment visit in Stage 2.

2.10 Dose-limiting Toxicity (Stopping Rules for an Individual Subject)

Toxicity will be graded and recorded according to the NCI CTCAE version 4.03 (US Department of Health and Human Services, 2010), which are considered at least possibly related to PRV111 Patch. A DLT is defined as a clinically significant Treatment-Emergent AE (TEAE) or laboratory abnormality unrelated to disease progression, concurrent illness, or concomitant therapy and that meets any of the following criteria:

- Grade 3 or 4 non-hematologic toxicity excluding alopecia
- Grade 3 or 4 nausea, vomiting, or diarrhea, lasting >48 hours, despite standard prophylaxis and/or treatment
- Grade 4 neutropenia lasting >5 days.
- Febrile neutropenia, defined as absolute neutrophil count <1000/mm³ with a single temperature of >38.3°C (101°F) or a sustained temperature of ≥38°C (100.4°F) for more than 1 hour.
- Grade 4 thrombocytopenia or thrombocytopenia with clinically significant bleeding (ie, bleeding that requires blood or platelet transfusion or other medical intervention, or that may cause disability or death, such as cerebral hemorrhage).
- Any grade 3 or 4 toxicity related to the study drug that precludes administration of at least 3 of the 4 planned applications.
- Grade 4 local toxicity- oral mucositis according to World Health Organization scale:
 - Grade 0 - No oral mucositis
 - Grade 1 - Erythema and soreness
 - Grade 2 - Ulcer, able to eat solids
 - Grade 3 - Ulcers, requires liquid diet (due to mucositis)
 - Grade 4 - Ulcers, alimentation not possible (due to mucositis)
- Any treatment related AE leading to surgery delay for more than 96 hours is a DLT

2.11 Schedule of Events

Table 2. Schedule of Events

	Screening Within 28 Days Prior to Visit 1	Days					Surgery	Months Post Surgery
		Treatment Visits				Post Treatment Pre-Op		Standard of Care (SOC) Follow-up
		Visit 1	Visit 2	Visit 3	Visit 4	Visit 5		Visit 6
	0	1	≥48 and ≤ 144 hours, post previous visit			≥72 hours post last treatment	≤42 days post Visit 1	1, 3, & 6 months (all can be +/-3 weeks) SOC visits
Confirmed SCC	X							
Informed consent	X							
Inclusion/exclusion criteria	X	X ^a						
Schedule study visits	X	X	X	X	X	X		
Demographic, medical/history	X							
Physical examination, ^{b,s} VS ^c	X	X ^a	X ^a	X ^a	X ^a	X		X
Anti-emetics		X ^a	X ^a	X ^a	X ^a			
██████ ^l	X							
Oral cavity examination ^d	X	X ^a	X ^a	X ^a	X ^a	X		X
Neck lymph nodes exam	X	X ^a	X ^a	X ^a	X ^a	X		X
ECG ^s	X					X		
██████████ ████████ ^l	X					X		
Clinical labs ^f	X	X ^a		X ^a		X	X ^o	
HPV ^s	X ^g							
Pregnancy test	X ^h	X ^a			X			
PK sampling		X ⁱ	X ^j	X ^j	X ⁱ			
Tumor resection							X ^k	

	Screening Within 28 Days Prior to Visit 1	Days					Surgery	Months Post Surgery
		Treatment Visits				Post Treatment Pre-Op		Standard of Care (SOC) Follow-up
		Visit 1	Visit 2	Visit 3	Visit 4	Visit 5		Visit 6
	0	1	≥48 and ≤ 144 hours, post previous visit		≥72 hours post last treatment	≤42 days post Visit 1	1, 3, & 6 months (all can be +/-3 weeks) SOC visits	
PRV111 patch treatment		X ^p	X ^p	X ^p	X ^p			
Tumor measurements ^q		X ^a	X ^a	X ^a	X ^a	X		
Tumor Volume change from baseline (CFB) criteria			X ^a	X ^a	X ^a	X		
Tumor photographs		X ^l	X ^l	X ^l	X ^l	X		
Loco-regional recurrence							X	
Histology ^s	X ^m					X ^m		
Technical success ⁿ		X	X	X	X			
Concomitant therapy	X	X	X	X	X	X	X	
AE assessment	X	X	X	X	X	X ^r		

Abbreviations: AE=adverse event; [redacted]; ECG=electrocardiogram; HPV=human papilloma virus; [redacted]; PE=permeation enhancer; PK=pharmacokinetics; SCC=squamous cell carcinoma; VS=vital signs.

- a Performed prior to dosing.
- b If a physical exam was performed within 14 days prior to the screening visit, it does not need to be repeated at the screening.
- c VS: seated blood pressure and pulse will be measured after the subject has been sitting for at least 3 minutes, respiration, temperature, height and weight will be recorded at every visit. VS will be obtained pre-dose at all visits and subject will also be monitored at 30+5 minutes, 60+5 minutes and 120+5 minutes following application of the last patch applied at Visits 1 and 4 and at 30+5 minutes post last patch application at Visits 2 and 3.
- d Take photos of the tumor region for further assessment of tumor shrinkage.
- e Every attempt should be made to use the same test for each subject for both timepoints.
- f CBC and chemistry panel (creatinine to determine the creatinine clearance, BUN, LFT, electrolytes (potassium, magnesium, calcium, and sodium), urinalysis.
- g Tissue will be collected at Screening but the HPV status will be ascertained at any time during the study using immunohistochemistry for p16 according to institutional clinical protocols.
- h Serum pregnancy test to establish eligibility for female subjects of childbearing potential. A negative urine pregnancy test must be documented within 7 days prior to the first treatment visit, and at Visit 5.
- i Visit 1 & 4: PK blood samples for total platinum collected pre- treatment (time -15 to 0 minutes), and 30±5 minutes, 60±5 minutes and 120±5 minutes post removal of last patch.
- j Visit 2 & 3: PK blood samples for total platinum collected pre- treatment (time -15 to 0 minutes), and 30±5 minutes, post removal of last patch and PE application.
- k Sampling for tumor and lymph nodes (if available) platinum levels.

- l Photos need to be taken prior to patch application.
- m Confirmation of tumor histology by a clinical pathologist is required prior to enrollment. A final pathology report, issued by a clinical pathologist is required following surgical resection of the tumor specimen.
- n Taste of the PE solution and patch, adhesion, peel-off, residual cisplatin level in the patch.
- o Performed after surgery if possible
- p PE should be applied to the tumor area prior to first patch and allow to stay for 5 minutes. Then applied again to the tumor area for 1 minute. Note that the mouth should be kept open for the saliva not wash off the PE.
- q Use "0.05" cm for the "Height" of a flat tumor. If a concave tumor, the "Height" can be shown as a negative number. If a non-measurable dent, use "-0.05" cm.
- r Only SAEs within 30 days post visit 5 need to be recorded.
- s. May use historical SOC information prior to consent if collected within 28 days prior to first treatment.

2.12 Study Endpoints

2.12.1 Primary Endpoints

The primary endpoints for the study involve determination of a safe and efficacious dose of PRV111 (Cisplatin Transmucosal System) (cisplatin drug-loaded patch + PE) under the conditions of the trial. Therefore, the primary endpoint is based on the incidence of DLTs and tumor volume change from baseline (CFB).

2.12.2 Secondary Endpoints

Based on secondary objectives, the secondary endpoints are:

- Evaluate tumor response
 - [REDACTED]
 - [REDACTED]
- Assess short and long-term safety of the treatment
 - Loco-regional control: subjects will be followed-up for disease recurrence and safety following surgery
 - Incidence of recurrence at 6 months
- Total platinum assessment in blood, tumor and lymph nodes (if available)
- Technical Success
 - Successful adhesion of the patch to the target lesion
 - Successful delivery (including release and permeation) of the drug to the target lesion, without getting to surrounding oral surfaces
 - Successful peel of the used patch after 10 minutes without damaging the target lesion underneath
 - Adhesion of the backing to the polymeric matrix embedded CLPs
 - Taste of the PE solution
 - Taste of the PRV111 patch
 - Residual cisplatin level in the patch after the application period

3 Efficacy Assessments

Efficacy outcomes include:

- Response to treatment evaluated by Tumor volume change from baseline (CFB)
- [REDACTED]
- Incidence of recurrence at 6 months
- Histological effect of PRV111 on the tumor tissue

3.1 PRIMARY: Tumor Photography and Measurements

The primary lesion will be photographed before PRV111 treatment. This will be done to allow for a clinical assessment of response to treatment. For details refer to Study Manual for instructions.

The tumor will be measured in cm to 1 digit to the right of the decimal point using a disposable plastic ruler or caliper. Three dimensions must be recorded (Length x Width x Height).

Note: If tumor or cancerous lesion is flat, a small number (0.05 cm) will be recorded for the Height. If the tumor is a concave, a negative Height is recorded. If the height is an unmeasurable dent, it can be recorded as (-0.05 cm). The volume calculations use the heights absolute value. The following formula will be used to calculate tumor volume (cm³)

$$L \times W \times H \times \pi/6$$

3.1.1 PRIMARY: Response and Non-Response (Tumor Volume Change from Baseline Criteria)

The terms “response” and “non-response” will be defined according to the tumor volume change from baseline (CFB) criteria:

$$\text{PCFB} = \% \text{ tumor volume change from the baseline}$$

Response will be defined as CR, SR, or PR. Non-Response will be defined as SD or PD.

Clinical Response to Treatment

Table 2. The Efficacy Criteria

Complete Response (CR)	Disappearance of primary lesion.
Partial Response (PR)	PCFB: $\geq 30\%$ to 69% decrease in the total tumor volume shrinkage (as determined by clinical measurement, taking as reference the baseline volume.
Strong Response (SR)	PCFB: $\geq 70\%$ to 99% decrease in the total tumor volume shrinkage (as determined by clinical measurement, taking as reference the baseline volume.
Progressive Disease (PD)	PCFB: At least a 20% increase tumor volume as determined by clinical measurement taking as reference the baseline volume (Note: the appearance of one or more new lesions is also considered progression).
Stable Disease (SD)	Neither sufficient shrinkage to qualify for PR nor sufficient increase to qualify for PD, taking as reference the volume determined by clinical measurement at baseline

[figure not shown]
3.1.2 Primary Efficacy Analysis

[figure not shown]
[figure not shown]
[figure not shown]
The primary efficacy variable is response according to the Tumor Volume criteria per agreement from the FDA. (Section 7.3.1), where a response is CR, SR or PR (ORR; Objective Response Rate) and a non-response is SD or PD (See Efficacy Criteria table). The primary analysis is the analysis using the Efficacy Population and tumor volume change from baseline (CFB). Include 95% CI for CFB tumor size. The study will be deemed a success if at least 7 of the up to 11 evaluable subjects achieve a minimum of a PR.

[figure not shown]
Change of tumor volume will be summarized for each visit, however the final efficacy determination will be based on CFB from V1 to V5.

[figure not shown]
A frequency distribution of efficacy based on overall response rate (ORR) at each visit will be provided evaluable population. A one-sided test of response (CR, PR, SR) rate less than 30% will be calculated at each visit.

Photographs from V1 vs V5 will be presented

[figure not shown]

3.2.2 SECONDARY: Loco-regional Control

Subjects will be followed-up for 6 months, and the incidence of local and regional (nodes) tumor recurrence will be recorded.

A summary table will show if any tumor recurred in the evaluable patients at 1,3, and 6 month follow up visits. The final analysis will include the summary of the incidence of tumor recurrence and survival status for the Efficacy of Evaluable Population.

[figure not shown]
Time to recurrence and time to death will be summarized, with Kaplan-Meier curves will be described in the CSR and corresponding summary statistics at months 1, 3 and 6.

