#### Figure 5. Stage 2b safety and efficacy scheme

*Note:* The surgery is to be performed no later than 42 days post Visit 1.

All subjects will subsequently undergo standard of care, surgical ablation of the tumor and satellite nodes, and possibly additional radiotherapy and chemotherapy. All subjects will be followed for up to 6 months post-surgery at 3 visits: 1 month, 3 months, and 6 months post-surgery for loco-regional response and safety. Follow-up visits may coincide with standard of care follow-up visits, if deemed appropriate by the Principal Investigator.

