#### 10.5.5 Efficacy Data

Efficacy outcomes include:

- Response to treatment evaluated by Tumor volume change from baseline (CFB)
- •
- Incidence of recurrence at 6 months

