5.3 Safety Analyses

The Safety Population will be used for all summaries of safety data.

will be used in the calculation of the incidence of individual TEAE by relationship.

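### Recurrence is labelled both safety and efficacy, but SAP 3.2.2 limits its table and the survival-status summary to the Evaluable Population, so the reported rate is not the rate in treated subjects

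*SAP*

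**What the plan says.** **Label.** SAP 2.12.2 and Protocol 10.5.4 have a secondary-endpoint heading "Assess short and long-term safety of the treatment". Under it they place "Loco-regional control: subjects will be followed-up for disease recurrence and safety following surgery" and the incidence of recurrence at 6 months. Other places call the same outcome efficacy: the Synopsis list of efficacy criteria, Protocol 9.2.5 (within 9.2, Efficacy Assessments), Protocol 10.5.5 ("Incidence of recurrence at 6 months") and the opening list of SAP section 3.

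**Population.** SAP 5.3 states: "The Safety Population will be used for all summaries of safety data". That population needs one applied patch (Protocol 10.4.1, SAP 5.3.1). The Evaluable Population needs all eligibility criteria met and 75% of the dose, which SAP 5.2.2 defines as at least 3 of the 4 treatment visits. It is the set named for efficacy (Protocol 10.4.2, SAP 5.2.2).

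**Planned output.** SAP 3.2.2 contains three displays:
- By visit: "A summary table will show if any tumor recurred in the evaluable patients at 1,3, and 6 month follow up visits".
- Final: "The final analysis will include the summary of the incidence of tumor recurrence and survival status for the Efficacy of Evaluable Population". The population name is garbled, but the Evaluable Population is the only efficacy set the SAP defines, so it must be meant.
- Time to event: "Time to recurrence and time to death will be summarized, with Kaplan-Meier curves will be described in the CSR". The sentence names no population.

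**Follow-up.** Protocol 6.1 says "All subjects will be followed for up to 6 months post-surgery at 3 visits", and 9.6.8 repeats it. Protocol 8.4 keeps a subject with a dose-limiting toxicity (DLT) in the study for data collection after dosing ends.

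**The concern.** If recurrence is a long-term safety outcome, its main summaries use the wrong population under the SAP's own rule. The set they do use is selected on completed treatment. A subject who stopped after one or two visits because of toxicity or progression goes to surgery, is followed to month 6, and is then left out of the recurrence table and the survival-status summary.

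The selection can be related to the treatment. One DLT criterion in Protocol 8.2 is toxicity that prevents at least 3 of the 4 planned applications. If that word means treatment visits there, the criterion largely describes a subject who fails the 75% rule. Protocol 7.3 also allows withdrawal for intolerability or disease progression.

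Little else summarises outcome to month 6. The schedule of events has no adverse-event assessment at Visits 7 to 9. SAE recording ends 30 days after Visit 5 (Protocol 9.3.6.6, SAP 4.6.9) or 30 days after surgery (SAP section 4). The listings named in SAP 4.7.1 do not include recurrence. SAP 3.2.2 is therefore the main planned account of what happens after surgery in a first-in-human study.

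**Working it through.** **The plan's own figure.** Neither document states a figure for recurrence or survival. The only design calculation is the two-stage response test. Summing Bin(5, x, p) × P(Bin(6, p) ≥ 7 − x) over x = 3 to 5 gives 0.0180 at p = 0.30 and 0.9644 at p = 0.85, which match the stated 0.018 and 96.44%. This point does not touch that test.

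**Text comparison.**
1. Under the safety label (SAP 2.12.2), SAP 5.3 requires the Safety Population. SAP 3.2.2 uses the Evaluable Population. These conflict.
2. Under the efficacy label (SAP section 3), SAP 5.2.2 names the Evaluable Population. SAP 3.2.2 agrees.
3. The plan does not say which label governs, and it gives the Kaplan-Meier summaries no stated population.

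**How many could be left out.** Non-evaluable subjects allowed by the enrolment caps:
- Stage 1: 10 − 5 = 5 of 10 (50%).
- Stage 2 if the dose changes: 21 − 11 = 10 of 21 (48%). The 11 are evaluable subjects at the final dose, so these 10 could include Stage 2a subjects who were evaluable at a dose later abandoned.

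These are ceilings on enrolled subjects. They do not forecast treated subjects.

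**What leaving them out can do to the rate (assumed counts).** Let x of 11 evaluable subjects recur and let k treated subjects be left out, of whom j recur. The plan reports x/11; the all-treated rate is (x + j)/(11 + k), with j between 0 and k. I take x = 4, close to the one third cited as background in SAP 1.1. That figure includes distant metastasis and is not tied to 6 months, so I also show x = 2.

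| k left out | x = 4 (reported 36.4%) | x = 2 (reported 18.2%) |
|---|---|---|
| 1 | 4/12 to 5/12: 33.3% to 41.7% | 2/12 to 3/12: 16.7% to 25.0% |
| 2 | 4/13 to 6/13: 30.8% to 46.2% | 2/13 to 4/13: 15.4% to 30.8% |
| 5 | 4/16 to 9/16: 25.0% to 56.3% | 2/16 to 7/16: 12.5% to 43.8% |
| 10 | 4/21 to 14/21: 19.0% to 66.7% | 2/21 to 12/21: 9.5% to 57.1% |

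**Direction.** With x = 4 and k = 5, the all-treated rate exceeds 36.4% once 2 of the 5 recur (6/16 = 37.5%) and is lower if 0 or 1 recur (4/16 = 25.0%, 5/16 = 31.3%). The sign depends on outcomes the documents cannot supply.

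**Against sampling error.** The exact 95% interval for 4/11 is 10.9% to 69.2%. The exclusion adds uncertainty that this interval does not contain.

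**The case against.** The best defence is that SAP 3.2.2 sits inside the efficacy section and follows the rule for efficacy. Several places call recurrence efficacy, and the list of safety assessments in SAP section 4 omits it. This stands in part: the text is not a plain breach of SAP 5.3. It is an outcome with two labels that imply two populations. The defence does not explain why the two endpoints named under long-term safety should be summarised only in subjects who completed most of the treatment.

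A reader might infer more than the documents support:
- *That survival is a listed safety endpoint.* It is in neither list of secondary endpoints and first appears in SAP 3.2.2.
- *That deaths vanish.* SAP section 4 and 4.7.1 plan listings of deaths, and a fatal event recorded as a serious treatment-emergent event would enter that table too. How complete these are for late deaths is unclear given the SAE windows, but that is a data-collection question which a change of population would not settle.
- *That every recurrence and survival display excludes these subjects.* The Kaplan-Meier sentence names no population. The figure at that place could not be read, so a label there cannot be ruled out.
- *That 15 of 31 treated subjects could be missing.* That sum (5 + 10 of 10 + 21) turns caps on enrolment into treated counts and pools doses, whereas the Synopsis presents summaries by dose as appropriate. Subjects enrolled without receiving a patch are in neither population.
- *That the reported rate is biased downward.* This is plausible for subjects stopped for toxicity or progression. But subjects are also non-evaluable for failing eligibility, which has no established link to recurrence.

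A further objection is sound. Recurrence presupposes resection, and some treated subjects may withdraw, be lost or never reach surgery. Counting them in the denominator as free of recurrence would lower the rate artificially, so a change of population needs a rule for them. It is also fair that these are descriptive displays with no test or decision attached.

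**Conclusion.** The point holds in a limited form. Under the safety label, SAP 3.2.2 conflicts with SAP 5.3; under the efficacy label it does not, and the plan leaves the choice open. Whichever label governs, the recurrence table and the survival-status summary leave out treated and followed subjects, partly on a criterion that toxicity can cause. The resulting rate describes subjects who met eligibility and completed at least 3 of 4 visits, and it cannot be quoted as the rate in treated subjects.

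The size depends on how many treated subjects turn out non-evaluable, which is unknown. With the assumed 4/11 and 5 left out, a reported 36% is compatible with an all-treated rate of 25% to 56%; with one left out the range is 33% to 42%. The direction is not established. The response test, its error rate and its power are unaffected. The change should be made because it is cheap and removes selection on completed treatment; the trial's main conclusion does not depend on it.

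**What to change.** In SAP 3.2.2:
1. Present the recurrence table, survival status and the Kaplan-Meier summaries for time to recurrence and time to death in the Safety Population, by dose.
2. Keep the Evaluable Population as a supportive display.
3. Name the population for the Kaplan-Meier curves explicitly.
4. Report treated subjects who were not resected, and those lost to follow-up or withdrawn, as separate categories in the recurrence table and as censored in the Kaplan-Meier analysis. Do not count them as recurrence-free. State the date from which time is counted, since a subject never resected has no surgery date.
5. Add a sentence that recurrence appears under both safety and efficacy and that the Safety Population governs its main summary.

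The cost is SAP wording and one additional table. Follow-up is already planned for all subjects, although withdrawal and loss will leave gaps, which item 4 makes visible. The recurrence rate may look less favourable.
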